# 15.1 Acceptable Concomitant Medications

With the exception of medications specifically prohibited in Exclusion Criteria 3 and 6, and during the treatment period of this study (see Section 15.2), patients are permitted to receive any supportive medications and treatments to manage ongoing medical conditions or AEs. Patients may receive red blood cell and platelet transfusions, or other hematopoietic support (i.e. growth factors) as needed during study participation *after eligibility has been determined* and the patient has been enrolled into the trial.

#### 15.2 Prohibited Concomitant Medications

Medications or vaccinations specifically prohibited in the exclusion criteria are not allowed during the ongoing trial. If there is a clinical indication for any medication or vaccination specifically prohibited during the trial, discontinuation from study intervention or vaccination may be required. The investigator is to discuss prohibited medication/vaccination with the Sponsor's Clinical Director. The final decision on any supportive therapy or vaccination rests with the investigator and/or the participant's primary physician. However, the decision to continue the participant on study treatment requires the mutual agreement of the investigator, the Sponsor and the participant.

Listed below are specific restrictions for concomitant therapy or vaccination during the course of the study: (Note: There are no prohibited therapies during the post-treatment long-term follow-up period).

- Anti-cancer systemic chemotherapy or biological therapy other than those specified in the protocol (GX-188E, pembrolizumab)
- Immunotherapy not specified in this protocol
- Chemotherapy not specified in this protocol
- Investigational agents other than Use of investigational therapeutic agents than those specified in the protocol (i.e., investigational regimen; GX-188E, pembrolizumab).
- Radiation therapy
  - Note: Radiation therapy to a symptomatic solitary lesion, to the brain, or for palliative purposes may be allowed after consultation with Sponsor Medical Monitor.
- Live or live attenuated vaccines within 30 days prior to the first dose of trial treatment and while participating in the trial.

Note: Administration of killed vaccines are allowed.

Note: Any licensed COVID-19 vaccine (including for Emergency use) in a particular country is allowed in the study as long as they are mRNA vaccines, adenoviral vaccines, or inactivated vaccines. These vaccines will be treated just as any other concomitant therapy. Investigational vaccines (i.e., those not licensed or approved for Emergency Use) are not allowed.

• Systemic glucocorticoids for any purpose other than to modulate symptoms from an event of clinical interest of suspected immunologic etiology. The use of physiologic doses of corticosteroids may be approved after consultation with the Sponsor Medical Monitor. *Topical and inhaled steroids are permitted*.

• Red blood cell or platelet transfusion, and hematopoietic growth factors are not permitted within 4 weeks prior to the first dose of study medication. However, once a patient has met all eligibility criteria and has enrolled into the trial, hematopoietic support treatments are permitted.

Patients who, in the assessment by the Investigator, require the use of any of the aforementioned treatments for clinical management should be removed from the trial. Patients may receive other medications that the Investigator deems to be medically necessary.

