#### 10.7.2 Exclusion Criteria

Participants are excluded from the study if any of the following criteria apply:

- 1. Patient has disease that is suitable for local therapy administered with curative intent
- 2. Has a known additional malignancy that is progressing or has required active treatment within the past 3 years.
  - Note: Participants with basal cell carcinoma of the skin, squamous cell carcinoma of the skin, or carcinoma in situ (e.g., breast carcinoma) that have undergone potentially curative therapy are not excluded.
- 3. Patient is expected to require any other form of antineoplastic therapy while on study; including systemic chemotherapy, radiation therapy (except for palliative purposes) biological therapy, or immunotherapy not specified in this protocol.
- 4. Patient has a history of active central nervous system (CNS) metastases and/or carcinomatous meningitis.
- 5. Has received prior therapy with an anti-PD-1, anti-PD-L1, or anti PD-L2 agent or with an agent directed to another stimulatory or co-inhibitory T-cell receptor (e.g., CTLA-4, OX 40, CD137) and was discontinued from that treatment due to a Grade 3 or higher immune-related Adverse Event (irAE).
- 6. Patients with active autoimmune disease requiring systemic immunosuppressive treatment within the past 2 years (i.e. with use of disease modifying agents, corticosteroids or immunosuppressive drugs). Replacement therapy (eg, thyroxine, insulin, or physiologic corticosteroid replacement therapy for adrenal or pituitary insufficiency, etc.) is not considered a form of systemic treatment and is allowed.

- 7. Has had an allogeneic solid organ or allogeneic bone marrow transplant
- 8. Patient has had a prior, non-PD-1/PD-L1/PD-L2, anti-cancer monoclonal antibody (mAb) (e.g., bevacizumab, cetuximab, etc) within 4 weeks prior to the first dose of study medication or who has not recovered (i.e., ≤ Grade 1 or at baseline) from adverse events due to agents administered more than 4 weeks earlier.
- 9. Has received prior systemic anti-cancer therapy, including investigational agents within 4 weeks, or within 2 weeks for targeted small molecule therapies with a half-life of <48 hrs prior to the first dose of study medication

Note: Participants must have recovered from all AEs due to previous therapies to ≤Grade 1 or baseline. Participants with ≤Grade 2 neuropathy and/or ≤Grade 2 anemia may be eligible.

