# Table 4. Dose Modification and Toxicity Management Guidelines for Immune-related AEs Associated with Pembrolizumab.

#### General instructions:

- 1. For Severe and life-threatening irAEs, should be treated with IV corticosteroid should be initiated first corticosteroids followed by oral steroidsteroids. Other immunosuppressive treatment should be initiated begin if the irAEs cannot beare not controlled by corticosteroids.
- 2. Pembrolizumab must be permanently discontinued if the irAE does not resolve or the corticosteroid dose is not ≤10 mg/day within 12 weeks of the last pembrolizumab treatment.
- 3. The corticosteroid taper should begin when the irAE is  $\leq$  Grade 1 and continue at least 4 weeks.
- 4. If pembrolizumab has been withheld, pembrolizumab may resume after the irAE decreased to ≤ Grade 1 after corticosteroid taper.

	Toxicity grade (CTCAE v4.0 or			
	the most recent	Action with	Corticosteroid and/or	
irAEs	version)	pembrolizumab	other therapies	Monitor and follow-up
Pneumonitis	Recurrent Grade 2, Grade 3 or 4	Permanently discontinue	
 
Administer         corticosteroids         (initial dose of 1-2         mg/kg prednisone         or equivalent)         followed by taper
 
Add prophylactic         antibiotics for         opportunistic         infections
 
	
 
Monitor participants for signs and symptoms of pneumonitis
 
Evaluate participants with suspected pneumonitis with radiographic imaging and initiate corticosteroid treatment
 

Diarrhea / Colitis	Grade 2 or 3	Withhold	Administer     corticosteroids     (initial dose of 1-2     mg/kg prednisone     or equivalent)     followed by taper	Monitor participants for signs and symptoms of enterocolitis (ie, diarrhea, abdominal pain, blood or mucus in stool with or without fever) and of bowel
	Recurrent Grade 3 or Grade 4	Permanently discontinue		perforation (ie, peritoneal signs and ileus).  Participants with ≥ Grade 2 diarrhea suspecting colitis should consider GI consultation and performing endoscopy to rule out colitis.  Participants with diarrhea/colitis should be advised to drink liberal quantities of clear fluids. If sufficient oral fluid intake is not feasible, fluid and electrolytes should be substituted via IV infusion.
AST or ALT elevation or Increased Bilirubin	Grade 2 ª	Withhold	Administer corticosteroids (initial dose of 0.5- 1 mg/kg	Monitor with liver function tests (consider weekly or more frequently until liver

	1		I 1:	

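### The closing sentence of protocol 15.2 tells sites to remove from the trial any patient who needs a listed treatment, including care the same list permits, and conflicts with the opening of 15.2, 19.1 and 22.1.3

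*Protocol*

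**What the plan says.** Protocol 15.2 opens with what happens if a prohibited medication or vaccine becomes clinically indicated: "discontinuation from study intervention or vaccination may be required". The investigator discusses the case with the sponsor. Continuing study treatment then depends on the investigator, the sponsor and the patient all agreeing.

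A list of restrictions follows, and several entries carry their own permissions:

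- Radiotherapy: "Radiation therapy to a symptomatic solitary lesion, to the brain, or for palliative purposes may be allowed after consultation with Sponsor Medical Monitor".
- Systemic glucocorticoids: "The use of physiologic doses of corticosteroids may be approved after consultation with the Sponsor Medical Monitor".
- Transfusions and growth factors: barred in the 4 weeks before the first dose, but "once a patient has met all eligibility criteria and has enrolled into the trial, hematopoietic support treatments are permitted".

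The closing paragraph then says that patients who, in the investigator's assessment, "require the use of any of the aforementioned treatments for clinical management should be removed from the trial".

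Three other sections bear on this. Section 15.1 says "Patients may receive red blood cell and platelet transfusions, or other hematopoietic support (i.e. growth factors) as needed during study participation", once eligibility is settled and the patient is enrolled. The first sentence of 19.1 says that stopping study treatment is not the same as withdrawing from the study. Section 22.1.3 asks that patients who stop treatment without documented progression stay on the 9-weekly imaging schedule.

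**The concern.** The closing sentence is an instruction to sites, and it has two faults.

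The first is scope. It reaches back to every treatment named above it, with no carve-out for the uses that the list allows or may allow.

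The second is level. It moves the patient out of the trial, where the opening of 15.2 speaks of the study intervention and 19.1 keeps the two apart.

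A site that follows the words could take a patient off effective treatment because she needed a transfusion. It could also stop scanning a patient who has not progressed. The primary endpoint needs a response to be confirmed at least 4 weeks later, and SAP 15.1 leaves a patient whose best response could not be confirmed out of the ORR24 population. Early loss of imaging is therefore undesirable even if it is rare.

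**Working it through.** No sample size, power or error rate is involved, so the check is a comparison of texts.

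**Step 1: scope.** Each item that the 15.2 list permits or may permit, against the closing sentence.

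| Item in the list | Status in the list | Support elsewhere | Closing sentence read literally |
|---|---|---|---|
| Transfusion, growth factors after enrolment | Permitted | 15.1 permits them as needed | Remove from trial |
| Radiotherapy to a solitary symptomatic lesion, to the brain, or palliative | May be allowed after consulting the medical monitor | Exclusion criterion 3 (10.7.2): "radiation therapy (except for palliative purposes" | Remove from trial |
| Physiologic-dose corticosteroids | May be approved after the same consultation | None needed | Remove from trial |

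The first row is the clearest conflict. The permission stands in the bullet directly above the closing paragraph, and 15.1 repeats it.

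**Step 2: action and level.** Take a treatment that no exception covers, such as a live vaccine given during the study.

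- Opening of 15.2: stopping the study intervention may be required, and the three parties can agree to continue. The object is study treatment, and there is discretion.
- Closing sentence of 15.2: the patient should be removed. The object is the trial, and no discretion is stated.
- 19.1, first sentence: stopping treatment does not amount to leaving the study.
- 22.1.3: the events that end imaging are new anticancer treatment, progression, pregnancy, death, withdrawn consent and the end of the study. Removal for a concomitant medication is not among them.

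Narrowing the scope would therefore not repair the sentence. Its stated action still differs from the other three texts.

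**Step 3: what follow-up is exposed.**

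- *Survival.* Section 10.8 follows every patient for up to 1 year after treatment stops unless she withdraws consent or dies, and 16.13 sets contacts about every 4 months. This is protected.
- *End-of-study scan.* Section 16.12 asks for the end-of-study procedures within 28 days in everyone who stops treatment for any reason. They include a scan unless confirmed progression was the reason for stopping. Section 22.1.3 waives the scan at discontinuation if one was done in the previous 4 weeks.
- *Later 9-weekly imaging.* This is the part that a literal reading could cut short.
- *Who is exposed.* Patients who start new anticancer treatment stop imaging anyway under 22.1.3, and that covers the listed chemotherapy, immunotherapy and anticancer biologics. Section 15.0 counts radiation among antineoplastic therapies, so palliative radiotherapy may fall there too. That leaves mainly patients given hematopoietic support, corticosteroids or a live vaccine.

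**The case against.** The strongest reply is that no sensible site would read the sentence this way. The section is headed as prohibited medications, and its list is introduced as restrictions. For blood products and growth factors the restricted use is the pre-dose window only. The opening gives the final say on supportive therapy to the investigator or the primary physician. The sentence after the disputed one lets patients receive other medications judged medically necessary. To remove a patient for a transfusion, a site would have to ignore the preceding bullet and 15.1.

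Much of this stands for scope. The intended meaning can be inferred, so that half is a fault of literal wording and not evidence that anyone meant to remove patients for permitted care. It is not a full answer, because a permission for *other* medications does not cover the listed ones. None of it touches the level of the action.

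A reader might also infer more than the documents support:

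- *That the protocol otherwise always speaks of study treatment.* It does not. Section 19.1 also lists reasons for being withdrawn from the study, and 23.1 and 24.4 use study-level wording. The sound comparison is with the opening of 15.2, the first sentence of 19.1, and 22.1.3.
- *That the sentence contradicts the steroid treatment of immune-related events in Table 4*, whose general instructions say "If pembrolizumab has been withheld, pembrolizumab may resume after the irAE decreased to" a low grade after the taper. The 15.2 bullet restricts glucocorticoids only for purposes other than managing suspected immune events, so those steroids are not among the treatments referred to.
- *That imaging would certainly end.* It could. Sections 16.12 and 22.1.3 still ask for scans, and a site may follow them instead.

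**Conclusion.** The sentence is wrong as written, and the point is minor. It gives an action that conflicts with permissions in its own list and, even for prohibited treatments, with the opening of 15.2, the first sentence of 19.1, and 22.1.3.

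A reader might infer that it threatens the Part C result. The documents do not support that. For a response to be lost, a site must follow the sentence literally. The patient must have an unconfirmed response, no progression and no new anticancer treatment. The end-of-study scan must then be waived or done too early to confirm, with no later scan. Separately, 24.4 makes a patient whose treatment stops before 45 days for a non-toxicity reason non-evaluable and replaceable, so stopping early for permitted care could change the denominator. The documents give no rate for any of these steps, so the effect on ORR24 cannot be computed. I judge it small because several uncommon conditions must coincide.

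The conclusion assumes only that some sites will apply the words as they stand. The protocol itself foresees hematopoietic support during the study, so the conflict can arise in routine care.

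**What to change.** Replace the closing sentence of 15.2 with:

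> Patients who require a prohibited treatment not covered by the exceptions above should be discontinued from study treatment, unless the investigator, Sponsor and participant agree to continue; they remain on study for the EOS visit (16.12), imaging per 22.1.3 and survival follow-up per 16.13.

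This limits the rule to prohibited uses, restores the discretion given at the start of 15.2, and states the level correctly. The cost is one sentence in a protocol amendment. It needs no new visits or scans, because the cited sections already ask for that follow-up, and the SAP needs no change.

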# 16.0 STUDY PROCEDURES AND OBSERVATIONS

All procedures for Part A,B and C are identical. These procedures are described in table format in the Schedule of Events (Appendix 1)

# 16.1 Screening Evaluation

The following Screening assessments must be performed within 28 days before administration of any component of the investigational treatment regimen. Procedures listed below that are performed as part of the normal standard of care (SOC) and within 28 days prior to Week 1 Day 1 may be used for screening purposes. If there are clinically significant abnormal laboratory test results or suspicious laboratory results, at the discretion of investigator (1) one time re-test for subjects with screening purposes is allowed (2) For screen-fail subjects with same reason above, one time re-screen is allowed.

:

- 1. Sign and date an IRB/IEC-approved informed consent form before any study-specific (i.e., non-SOC) screening procedures are performed.
- 2. Demographic information including date of birth, gender, and ethnic origin
- 3. Medical history, including review of prior cancer treatments and documentation of HPV 16 or 18 positive cervical cancer. HPV-16 or HPV-18 positivity will be determined according to the patients' previous medical records or in situ PCR method using the patients' archival tissue sample or new biopsy tissue sample.
- 4. Review of concomitant medications
- 5. ECOG performance evaluation

- 6. Moore criteria evaluation (APPENDIX 3). Determine whether the patient is classified as low risk, mid risk, or high risk based upon Moore criteria
- 7. Complete physical examination including weight (kg) and height (cm)
- 8. Vital signs [sitting blood pressure, pulse rate, respiratory rate, and temperature]
- 9. Chest X-ray, ECG and Clinical laboratory evaluation (hematology, coagulation, serum chemistry, serology, urinalysis), including blood CEA/TA4 levels and thyroid function tests; see Appendix 4.
- 10. Serum or urine pregnancy test. This is only required for females of child-bearing potential and must be negative within 3 days prior to Week 1 Day 1.
- 11. Research blood collection. (including blood sample for Flt-3L level monitoring)
- 12. Pre-treatment tumor biopsy. All patients must submit either an archival tumor tissue sample or fresh biopsy sample at Screening. Coagulation tests must be performed and evaluated within 24 hr prior to all biopsy procedures.
- 13. Radiographic evaluation of tumor burden. Scans performed within 28 days of Week 1 Day 1 will be accepted and do not need to be repeated unless a clinically significant difference is suspected. See Appendices 5 and 6.

A patient who meets all of the inclusion criteria may enter the study. Screen failures will be reported into the Screen Failures Log.

# 16.2 Week 1 Day 1

At the Week 1 Day 1 visit, patients will return to the clinic for the first administration of GX-188E and P.

Patients will undergo the following procedures on Week 1 Day 1:

- 1. AE monitoring
- 2. Recording of concomitant medications
- 3. Vital signs and weight
- 4. Symptom-directed physical exam

- 5. Clinical laboratory evaluation (hematology, serum chemistry, urinalysis). The laboratory tests may not be performed repately if the screening tests were performed within 7 days of Week 1 Day 1 and the clinically significant changes for the results were not suspected.
- 6. Research blood collection. This sample must be obtained prior to the first dose of GX-188E and pembrolizumab.
- 7. Pain Assessment. Within 30 minutes before and 5 minutes (± 2 minutes) after GX-188E administration, pain score in association with the electroporation (EP) procedure should be reported.
- 8. Administration of GX-188E at both right and left deltoid muscles
- 9. Administration of pembrolizumab. For the purposes of this study, pembrolizumab should be administered *after* the GX-188E vaccination on all days in which patients are scheduled to receive both.

# 16.3 Week 2 Day 1 ( $\pm$ 3 days)

At Week 2 Day 1, patients will return to the clinic for administration of GX-188E (without pembrolizumab) and undergo the following procedures:

- 1. AE monitoring
- 2. Recording of concomitant medications
- 3. Vital signs and weight
- 4. Symptom-directed physical exam
- 5. Clinical laboratory evaluation (hematology and serum chemistry).
- 6. Pain Assessment. Within 30 minutes before and 5 minutes (± 2 minutes) after GX-188E administration, pain score in association with the electroporation (EP) procedure should be reported.
- 7. Administration of GX-188E at both right and left lateralis muscles

# 16.4 Week 3 Day 1 (±3 days)

Only safety evaluations will occur at the Week 3 Day 1 visit; no study drugs will be administered. Patients will undergo the following procedures on Week 3 Day 1:

- 1. AE monitoring
- 2. Recording of concomitant medications
- 3. Vital signs and weight
- 4. Symptom-directed physical exam
- 5. Clinical laboratory evaluation (hematology and serum chemistry).

# 16.5 Week 4 Day 1 ( $\pm$ 3 days)

At Week 4 Day 1, patients will return to the clinic for administration of GX-188E + P and undergo the following procedures:

- 1. AE monitoring
- 2. Recording of concomitant medications
- 3. Vital signs and weight
- 4. Symptom-directed physical exam
- 5. ECOG Performance Status
- 6. Clinical laboratory evaluation (hematology and serum chemistry).
- 7. Research blood collection.
- 8. Pain Assessment. Within 30 minutes before and 5 minutes (± 2 minutes) after GX-188E administration, pain score in association with the electroporation (EP) procedure should be reported.
- 9. Administration of GX-188E at both right and left deltoid muscles (or, lateralis muscles for Reduction Level 1)
- 10. Administration of pembrolizumab. For the purposes of this study, pembrolizumab should be administered *after* the GX-188E vaccination on all days in which patients are scheduled to receive both.

# 16.6 Week 7 Day 1 (±3Days)

At Week 7 Day 1, patients will return to the clinic for administration of GX-188E + P and undergo the following procedures:

- 1. AE monitoring
- 2. Recording of concomitant medications
- 3. Vital signs and weight
- 4. Symptom-directed physical exam
- 5. ECOG Performance Status
- 6. Clinical laboratory evaluation (hematology, serum chemistry, *and both blood CEA/TA4 levels and thyroid function tests*).
- 7. Research blood collection.
- 8. Pain Assessment. Within 30 minutes before and 5 minutes (± 2 minutes) after GX-188E administration, pain score in association with the electroporation (EP) procedure should be reported.
- 9. Administration of GX-188E at both right and left lateralis muscles (or, deltoid muscles for Reduction Level 1)
- 10. Administration of pembrolizumab. For the purposes of this study, pembrolizumab should be administered *after* the GX-188E vaccination on all days in which patients are scheduled to receive both.

